5. STUDY TREATMENT

5.1. ISOLYTE INF SOL

ISOLYTE INF SOL was chosen as a model preparation of crystalloid solution for intravenous administration in this clinical trial (ATC code: B05BB01). Detailed information on its pharmacodynamics, pharmacokinetics, excipients and other characteristics can be found in the [SmPC](#).

Quantitative composition:

	500 ml	1000 ml
Sodium Acetate Trihydrate	2.32 g	4.63 g
Sodium Chloride	3.01 g	6.02 g
Potassium Chloride	0.15 g	0.30 g
Magnesium Chloride Hexahydrate	0.15 g	0.30 g

Electrolytes: Na^+ 137.0 mmol/l, K^+ 4.0 mmol/l, Mg^{2+} 1.5 mmol/l, Cl^- 110.0 mmol/l, CH_3COO^- 34.0 mmol/l

5.1.1. Pharmaceutical form and route of administration

Solution for infusion; intravenous administration

5.1.2. Marketing-authorization holder

Fresenius Kabi s.r.o., [name], Česká republika

5.1.3. Storage

Shelf life in intact packaging (before opening): Freeflex - 3 years, KabiPac - 3 years. Protect from cold or frost.

5.1.4. Dosing schedule

Dosage will be chosen and adjusted according to the investigator's decision in accordance with SmPC. A detailed description of the recommended dosage is included in the Chapter 6.3.

5.1.5. Contraindication

Administration of IMP is contraindicated in cases of:

- fluid overload (hyperhydration; especially with pulmonary oedema and congestive heart failure),
- severe renal dysfunction,
- metabolic alkalosis and
- hyperkalemia.

5.1.6. Adverse effects

The following adverse effects have been reported during administration of electrolyte solutions:

1. Disorders of metabolism and nutrition

- hyperhydration and heart failure in patients with heart failure or pulmonary oedema (very common >1/10)
- oedema due to excess water/sodium in the body (frequency not known)

2. General disorders and reaction at the site of application

- febrile response, injection site infection, local pain or reaction, vein irritation, venous thrombosis or phlebitis extending from the injection site, and extravasation

At high doses, the dilution effect can often lead to dilution of individual blood components, e.g. coagulation factors and other plasma proteins, and to a decrease in hematocrit. In case of adverse effects, the infusion must be interrupted.

5.2. GELASPA^N 4% INF SOL

GELASPA^N 4% INF SOL was chosen as a model preparation of colloid solution for intravenous administration in this clinical trial (ATC code: B05AA06). Detailed information on its pharmacodynamics, pharmacokinetics, adverse effects, excipients and other characteristics can be found in the [SmPC](#).

Quantitative composition:

	1000 ml
Gelatin Succinate	40.0 g
Sodium Chloride	5.55 g
Sodium Acetate Trihydrate	3.27 g
Potassium Chloride	0.30 g
Calcium Chloride Dihydrate	0.15 g
Magnesium Chloride Hexahydrate	0.20 g

Electrolytes: Na⁺ 151.0 mmol/l, K⁺ 4.0 mmol/l, Mg²⁺ 1.0 mmol/l, Ca²⁺ 1.0 mmol/l, Cl⁻ 103.0 mmol/l, CH₃COO⁻ 24.0 mmol/l

5.2.1. Pharmaceutical form and route of administration

Solution for infusion; intravenous administration

5.2.2. Marketing-authorization holder

B. Braun Melsungen AG, [name], Germany

5.2.3. Storage

Shelf life in intact packaging (before opening): polyethylene bottles - 2 years, plastic bags (PVC-free) - 2 years. Store at a temperature of up to 25 °C. Protect from frost.

5.2.4. Dosing schedule

Dosage will be chosen and adjusted according to the investigator's decision in accordance with SmPC. A detailed description of the recommended dosage is included in the Chapter 6.3.

5.2.5. Contraindication

- hypersensitivity to solutions containing gelatin or to any of the excipients
- hypersensitivity to galactose- α -1,3-galactose (alpha-gal) or known allergy to red meat (mammal meat) and offal
- hypervolemia
- hyperhydration
- acute congestive heart failure

5.2.6. Adverse effects

The following adverse effects have been reported during administration of Gelaspan 4%:

- Very common ($\geq 1/10$): decreased hematocrit and decreased concentration of plasma proteins
- Common ($\geq 1/100$ to $<1/10$): relatively large doses of Gelaspan 4% cause dilution of coagulation factors and can therefore affect blood coagulation. After administration of large doses of Gelaspan 4%, the value of prothrombin time may increase and the activated partial thromboplastin time (aPTT) may be prolonged.
- Rare ($\geq 1/10,000$ to $<1/1,000$): anaphylactic/anaphylactoid reactions up to shock
- Very rare ($< 1/10,000$): tachycardia, hypotension, fever, chills
- Not known: nausea, vomiting, abdominal pain, decreased oxygen saturation

In the event of an anaphylactoid reaction, the infusion must be stopped immediately and the usual acute treatment instituted.

5.3. Prohibited medication

No prohibited medication is defined for the purposes of this clinical trial.

5.4. Concomitant medication

Fluids, vasopressors and inotropes listed in Chapter 6.3 (see detailed information on dosage) can be used to treat hypovolemia, hypotension and low cardiac output respectively.

6. COURSE OF THE TRIAL

6.1. Screening of eligible patients

Adult patients scheduled for elective neurosurgery will be screened for eligibility criteria after admission to the hospital. Study team members will perform the screening, and the principal investigator will regularly audit the accuracy of screening. Patients will be included if they meet all inclusion criteria and none of the exclusion criteria. After obtaining informed consent, each patient will be randomised to one of the trial arms. For details on obtaining the informed consent see Chapter 10.1.

6.2. Clinical examinations and assessments

During the trial course, subjects will be monitored during hospitalization and after discharge. A summary of scheduled procedures is outlined in Chapter 6.3. For a graphic summary see Table 1.

Table 1: Clinical trial schedule

	STUDY PERIOD						
	Screening	Allocation	Post-allocation		Hospital discharge	Follow-up	Premature termination
TIMEPOINT	D ₋₃₋₀		D ₁	D ₂	D ₃₋₂₈	D ₂₈	Anytime
ENROLMENT:							
Eligibility criteria	X						
Informed consent	X						
Pregnancy testing ¹	X						
Randomization		X					
ASSESSMENTS:							
Demographic data ²		X					
Fluid therapy ³			X	X			
Laboratory testing ⁴			X	X			
Hemodynamics ⁵			X	X*			
Adverse events			X	X	X	X	X
Postoperative complications (AESI ⁶)			X	X	X	X	X
Blood loss ⁷			X	X			
Urinary output ⁸			X	X			
Transfusion products consumption ⁹			X	X			
Duration of surgery (min)			X				
ICU LOS (days)					X		
LOS (days)					X		
28-day mortality						X	
Reason for premature termination							X

1 urine pregnancy testing

2 age, sex, weight

3 type and volume (ml) during surgery and in the 24-hour postoperative period (for more details see Chapter 2.3, point 4.)

4 hemoglobin, plasma lactate level (for more details see Chapter 2.3, point 3.)

5 MAP, HR, SVV, number of hypotension episodes, number of vasopressor administrations (for more details see Chapter 2.3, point 2.)

6 for more details see Chapter 2.2

7 volume (ml/kg) during surgery and in the 24-hour postoperative period

8 volume (ml/kg/hod) during surgery and in the 24-hour postoperative period

9 number of administered units of packed RBC during surgery and in the 24-hour postoperative period

*except SVV

6.3. Study procedures

Day -3 to 0

- Eligibility screen – inclusion and exclusion criteria
- Informed consent procedure (Chapter 10.1)
- Pregnancy testing (see Chapter 7.8)
- Demographic data
- Randomization (more in Chapter 4.3)

Day 1

- Assessment of hemoglobin and plasma lactate level
- Recording blood loss and urinary output during and after surgery
- Transfusion products consumption
- Crystalloid and colloid solution consumption
- Monitoring of hemodynamic parameters
- Monitoring of adverse events and reactions including postoperative complications of special interest

Prior to surgery, study participants will receive regular premedication according to hospital standards.

General anaesthesia will be induced by intravenous administration of propofol. For attenuation of the hemodynamic response to laryngoscopy, opioid will be added. To facilitate intubation, a neuromuscular blocking agent (N MBA) will be used. After tracheal intubation, mechanical ventilation will be commenced with the following settings: tidal volume of 8–10 ml/kg and respiratory rate to maintain an end-tidal CO₂ of 30–35 mmHg. Anaesthesia will be maintained with propofol infusion using TCI (target controlled infusion) or TIVA (total intravenous anaesthesia) and additional doses of opioids and relaxants will be administered at the discretion of the attending anaesthesiologist. The patients' temperature will be maintained at 36–37 °C.

Both groups will receive standard monitoring of vital signs through continuous electrocardiography, pulse oximetry, end-tidal CO₂ measurement, and invasive monitoring of arterial blood pressure.

In the STANDARD arm, perioperative hemodynamic management and postoperative care will be at the discretion of the attending anaesthesiologist and intensivist, respectively. Hypotension with MAP < 65 mmHg will be managed with administration of a 250-ml bolus of balanced crystalloid over 10 min or 250-ml bolus of colloid over 5 min. The choice of fluid and number of boluses will be at the discretion of attending anaesthesiologist. If fluids are considered ineffective, a vasopressor will be added.

In the GDHT arm, non-invasive hemodynamic monitoring will be used (Starling™ SV hemodynamic monitor, Cheetah Medical Inc., [name], USA) in addition to the monitoring used in the STANDARD arm. The Starling SV monitor uses

patented Bioreactance® technology and requires placement of only four sensors, which are skin electrodes similar to those used for ECG monitoring.

The extended monitoring will begin after the induction of general anaesthesia and resolution of any hypotension caused by the induction of general anaesthesia. This hypotension will be resolved with fluid bolus and vasopressor administration if necessary. Subsequently, a basal infusion will be initiated with balanced crystalloid solution at $3 \text{ ml.kg}^{-1}.\text{h}^{-1}$ with an infusion pump. We will then determine the optimal Cl^a , defined by a value of at least $2,5 \text{ l.min.m}^{-2}$, a stroke volume variation (SVV) below 15%, and a MAP above 65 mmHg. If the Cl^a will not be optimal, appropriate interventions will be performed to achieve optimal values.

In case of $\text{SVV} > 15\%$, a 250-ml bolus of crystalloid over 10 min will be administered. This process will be repeated until the SVV decrease below 15%. If the SVV is above 15%, and the Cl^a decrease with administration of a bolus of crystalloid, inotropic therapy will be introduced (dobutamine) at a dose of 2,5 mcg/kg/min and increased if necessary to achieve $\text{Cl}^a > 2,5 \text{ l.min.m}^{-2}$

If hypotension occurs with MAP below 65 mmHg and SVV below 15%, norepinephrine therapy will be initiated.

After determining the optimal Cl^a , we will aim to maintain the SVV below 15% to preserve the optimal Cl^a . When the SVV exceed 15%, and the Cl^a is lower than optimal, a crystalloid bolus (250 ml) will be administered. If, after administration of crystalloid, the SVV decrease below 15%, the Cl^a will be verified. If the Cl^a is optimal, no further action will be taken. If the Cl^a remain suboptimal, the crystalloid bolus will be repeated.

If the SVV remain above 15% despite crystalloid bolus administration, the Cl^a will be verified. If the Cl^a increase, no further action will be taken. If the Cl^a is suboptimal, inotropic therapy will be introduced (dobutamine).

In case of hypotension with MAP below 65 mmHg concurrent with an SVV above 15%, a 250-ml balanced crystalloid bolus will be administered. If hypotension with MAP below 65 mmHg and SVV below 15% occurs, norepinephrine therapy will be started.

Day 2

- Assessment of hemoglobin and plasma lactate level
- Recording blood loss and urinary output during and after surgery
- Transfusion products consumption
- Crystalloid and colloid solution consumption
- Monitoring of hemodynamic parameters except SVV
- Monitoring of adverse events and reactions including postoperative complications of special interest

Day 3 to Day 28 / ICU discharge (whichever comes first)

- Checking adverse events and adverse reactions (with special interest in postoperative complications of special interest)
- Discharge from ICU and hospital

Day 28

- Checking adverse events and adverse reactions (outpatient or telephone call)
- Mortality assessment

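### In the maintenance phase of the GDHT algorithm, a cardiac index that rises but stays below 2.5 while SVV remains above 15% meets two opposing instructions, and 'optimal' index is ambiguous

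*Protocol*

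**What the plan says.** Protocol section 6.3 describes two phases for the GDHT arm.

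**Optimisation.** An 'optimal' cardiac index is determined. It is listed as a value of at least 2.5 l/min/m² together with "a stroke volume variation (SVV) below 15%, and a MAP above 65 mmHg". While SVV exceeds 15%, 250-ml crystalloid boluses are given. If the index falls with a bolus, dobutamine is started and titrated to an index above 2.5.

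**Maintenance.** Once the optimal index has been determined, the stated intention is that "we will aim to maintain the SVV below 15% to preserve the optimal Cl^a". The ordinary bolus has two conditions: "When the SVV exceed 15%, and the Cl^a is lower than optimal, a crystalloid bolus (250 ml) will be administered". Two branches follow:

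- SVV falls below 15%: the index is checked and left alone if optimal. Otherwise, "If the Cl^a remain suboptimal, the crystalloid bolus will be repeated".
- SVV stays above 15%: the index is checked, and "If the Cl^a increase, no further action will be taken. If the Cl^a is suboptimal, inotropic therapy will be introduced (dobutamine".

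A separate rule covers low pressure: "In case of hypotension with MAP below 65 mmHg concurrent with an SVV above 15%, a 250-ml balanced crystalloid bolus will be administered".

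Sections 8.2 and 8.6 analyse the primary endpoint in both the FAS and the PPS. The principal investigator judges protocol non-adherence for the PPS case by case.

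**The concern.** The branch for SVV still above 15% has two tests that do not divide patients cleanly. One asks whether the index went up, the other whether it is below optimal. An index can do both. Nothing says which sentence prevails, and one means leaving the patient alone while the other means starting an inotrope.

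Three things are at stake.

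- **Delivery.** The algorithm is the tested intervention in a trial planned as multicentre (section 3). Two sites could each follow the text and treat the same patient differently.
- **Adherence.** In the conflicted state either action obeys one sentence and departs from the other, so the text gives no standard for judging that episode for the PPS.
- **Visibility.** The haemodynamic parameters listed in section 2.3 and Table 1 are MAP, HR, SVV, hypotension episodes and vasopressor administrations. Neither cardiac index nor inotrope use is listed, so different handling might not show in the planned summaries.

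Arrhythmia, cardiogenic pulmonary oedema and brain oedema are components of the primary endpoint (section 2.2). How fluid and inotropes are used is therefore not remote from it.

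**Working it through.** No figure in the plan is disputed, so the check is a comparison of the sentences in section 6.3.

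**Inputs.** The definition of 'optimal', the maintenance bolus trigger, the two sentences for SVV still above 15% after a bolus, and the hypotension bolus rule.

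**Step 1: readings of 'optimal'.** The listed definition allows at least two:

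- *Floor reading*: the index is optimal if it is at least 2.5.
- *Three-part reading*: it is optimal only if the index is at least 2.5, SVV is below 15% and MAP is above 65 mmHg.

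A third possibility is a patient-specific index value, fixed once the three conditions have been met. It behaves like the floor reading with that value in place of 2.5.

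**Step 2: states.** In maintenance, with SVV above 15% after a bolus and MAP not below 65 mmHg, the index either rose or did not, and is either at least 2.5 or below it. That gives 2 × 2 = 4 states.

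| Index after the bolus | Floor reading | Three-part reading |
|---|---|---|
| Rose, still below 2.5 | no action **and** dobutamine | no action **and** dobutamine |
| Rose, at least 2.5 | no action | no action **and** dobutamine |
| Did not rise, at least 2.5 | no instruction | dobutamine |
| Did not rise, below 2.5 | dobutamine | dobutamine |

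The first row conflicts under both readings. Under the three-part reading the second row conflicts as well, because an index cannot be optimal while SVV exceeds 15%.

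**Step 3: which states can be reached.** Under the floor reading, the ordinary maintenance bolus requires an index already below 2.5. An index that did not rise must then still be below 2.5, so the third row cannot follow that bolus. It can arise only after the hypotension bolus, which is given whatever the index. On the ordinary route three states remain, and one of them (a partial response) is contradictory. Under the three-part reading, SVV above 15% already makes the index 'lower than optimal', so all four states are reachable and two conflict.

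**Step 4: comparison with the neighbouring branch.** Where SVV falls below 15%, both tests are on level (optimal, or still suboptimal), and the two outcomes are exclusive. Only the branch with SVV still above 15% mixes change with level.

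**Step 5: what is not counted.** The optimisation rule "This process will be repeated until the SVV decrease below 15" per cent belongs to the other phase. The repeat-bolus sentence in maintenance applies after SVV has fallen below 15%. Neither contradicts the branch examined here.

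**The case against.** The strongest reply is that a sensible clinician would resolve the pair of sentences. Two charitable readings exist. In one, a rise means a rise to the optimal value, parallel to the branch before it; a partial response then leads to dobutamine. In the other, the tests run in order, so any rise ends the matter and only a patient without a rise is tested for level; a partial response then leads to no action. Each reading is coherent, but they give opposite actions for the same patient. The conflict stands.

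Other replies succeed against stronger inferences that a reader might draw.

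- *That 'optimal' is circular.* Maintenance tests SVV and the index as separate conditions. If 'optimal' already required SVV below 15%, the second condition would be empty. Dobutamine is also titrated to the index value alone. The documents support 'ambiguous', not 'circular'.
- *That half of the four states lack a unique action.* This gives the states equal weight and ignores the entry condition in Step 3. It also cannot be combined with the claim that every state is suboptimal, because the two claims need different readings.
- *That GDHT is not one defined treatment.* Section 6.3 fixes the index floor, the SVV and MAP thresholds, the bolus volume, the basal rate, the dobutamine starting dose and the norepinephrine trigger. The defect is confined to particular states.
- *That PPS membership cannot be judged at all.* Section 8.6 provides case-by-case assessment, and FAS membership does not depend on following the algorithm. The difficulty is limited to episodes in the conflicted states.

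**Conclusion.** The point holds in a narrow form. In maintenance, with SVV above 15% after a bolus, section 6.3 gives two opposing instructions for an index that rose but is still below 2.5. This is so under either reading of 'optimal', and the ordinary bolus pathway leads there directly. Beyond that state the extent depends on the definition:

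- three conditions read together: the conflict covers every patient whose index rose while SVV stayed above 15%;
- 2.5 floor only: an index at or above 2.5 that did not rise after a hypotension bolus has no instruction.

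The state count assumes that MAP is not below 65 mmHg when the index is checked; otherwise the hypotension rule also applies.

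The documents do not say how often these states occur or how sites would act in them, so no effect on the event rates or power can be calculated. The sample size of 140 is not affected. This is a contradiction in the protocol's own treatment instructions and not a detail that can be left to the SAP.

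**What to change.** The sponsor must reconcile these sentences of section 6.3:

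1. State one definition of 'optimal' cardiac index and use it throughout the section, making clear whether the SVV and MAP limits are part of it.
2. Rewrite the branch for SVV still above 15% after a bolus so that its conditions are mutually exclusive and cover every case, including after a bolus given for hypotension.
3. Use the reconciled text as the reference when GDHT adherence is judged for the PPS under section 8.6.

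Which action belongs to which state is a clinical decision for the sponsor, and this review takes no position on it. A full table of every SVV, index and MAP combination is not needed to remove the defect. The cost is protocol wording and site training, with no extra patients or data.

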6.4. Biological samples

Blood samples will be taken following local practice and analysed in the respective clinical laboratory facility of the trial centre. No other biological specimens will be obtained or stored in this trial.

7. SAFETY ASSESSMENTS

Before the start of the clinical trial, all investigators will undergo training in pharmacovigilance requirements and procedures.

7.1. Definitions (according to the Regulation EU No. 536/2014)

For clinical trials, effective legislation has introduced the following definitions.

Table 2: Definitions of safety events

Adverse event	AE	Any untoward medical occurrence in a patient or clinical trial subject administered a medicinal product and which does not necessarily have a causal relationship with this treatment.
Adverse drug reaction	ADR	All untoward and unintended responses to an investigational medicinal product related to any dose administered
Serious adverse event	SAE	A serious adverse event/reaction is any untoward medical occurrence or effect that at any dose: 
• Results in death;• Is life-threatening;• Requires hospitalization or extension of existing hospitalization;• Results in persistent or significant disability or incapacity;• Is a congenital anomaly or birth defect.
Serious adverse reaction	SADR	
Unexpected adverse reaction	UADR	Adverse reaction, the nature, severity, or outcome of which is not consistent with the product information (SmPC)
Suspected unexpected serious adverse reaction	SUSAR	Any suspected adverse reaction related to the study treatment that is both serious and unexpected.

7.2. AE surveillance, recording and documentation

AE could be diseases or symptoms which occur or worsen after the enrolment of a patient in the clinical trial. All AEs need to be documented, no matter if the investigator suspects a causal

connection to the study medication. AE will be monitored and documented **from the day of giving informed consent until the end of participation in the study** (i.e., End of Study Visit or Premature withdrawal Visit).

Subjects will be instructed to report any AEs that they experience to the investigator. The investigator should actively ask about AEs and record the potential AE.

Each AE should be described, documented in the eCRF, and evaluated to determine:

- Seriousness (see Chapter 7.4);
- Severity (see Chapter 7.5);
- Causality, i.e. relation to the study medication (see Chapter 7.6);
- Duration (start and end dates or whether it continues).
- Action taken (no action taken; study medication discontinued; prolongation of the ongoing hospitalization; administration of a drug etc.)

AE needs to be **followed until its resolution**, i.e. until it subsides, stabilizes, becomes chronic, or the subject dies.

If AE fulfils the criteria of **SAE**, **separate form in eCRF** must be completed (see Chapter 7.7).

AEs will be recorded according to the Medical Dictionary for Regulatory Activities (MedDRA). The most recent MedDRA version at the start of the study will be used.

